When given concomitantly, camidanlumab tesirine will be administered prior to pembrolizumab, and separated by 1 hour.

Patients, who tolerate the combination and are in disease control, would be allowed to receive additional cycles of camidanlumab tesirine in combination with pembrolizumab, starting from Cycle 5. Additional administration of camidanlumab tesirine can be given per protocol upon informing the Sponsor.

Additional administration of camidanlumab tesirine concomitantly with pembrolizumab, will be given as follow: 2 consecutive Cycles every 2 Cycles (2 Cycles on, 2 Cycles off schedule), starting from Cycle 5 for up to a year (i.e., Cycle 5 and 6, Cycle 9 and 10, Cycle 13 and 14, Cycle 17 and 18) if there is no delay in the planned treatment schedule, or, in case of delay in the administration of pembrolizumab, after respecting a minimum of 63 days (9 weeks) between the last dose of camidanlumab tesirine and the first dose of the 2 subsequent additional administrations of camidanlumab tesirine. Between these cycles, patients should receive pembrolizumab as a single agent.

Sample Size:

Approximately 95 patients; Part 1 may enroll approximately 65 patients and Part 2 will enroll approximately 30 patients.

Statistical Considerations:

Safety and tolerability analyses will be presented descriptively. ORR with 95% CI from treated patients will be presented descriptively. Duration of response, PFS, and OS will be analyzed in Kaplan-Meier approach.

SCHEDULE OF EVENTS

Table 1. Schedule of Events Every 3 Weeks (Q3W) Dosing Schedule: Camidanlumab Tesirine as Monotherapy

	Protocol Section	Screening	Treatment Period						Follow-up Period (up to 1 year from EOT)	
(1 cycle = 21 days)			Cycle 1 and Cycle 2 (C1 and C2)				C3 and beyond		EOT	Every 12 weeks (wks)
Day (D)		-21 to -1	1	3 and 5	8	15	1	8 ¹		
Informed consent	11.3	X								
Eligibility criteria	5.1 5.2	X								
Demography and Baseline Characteristics	7.2	X								
Medical/Cancer history	7.2	X								
Fresh tumor tissue collection	7.5.3.2	X prior to 1 st dose (from non-target lesion)	Optional biopsy prior to C2D1 (-1 wk window) ² and preferentially from the same site as the Baseline biopsy. This biopsy is mandatory for paired-biopsy cohorts.							
Disease assessment	7.3	X ³	6 weeks and 12 weeks after C1D1, then every 12 wks ³						X ³	Every 12 wks from EOT until disease progression ⁴
Physical examination, incl. neurological examination and check for infection	7.4.1	X	X		X	X	X		X	

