4.1.1 Dose-Escalation

Dose-escalation cohorts:

In the dose-escalation part, patients will receive escalating doses of camidanlumab tesirine as monotherapy, or escalating doses of camidanlumab tesirine in combination with pembrolizumab, guided by a 3+3 design.

For each dose level (Section 6.3 and Section 6.4), if none of the first 3 patients at that dose level experience a DLT, new patients may be entered at the next higher dose level. If 1 of 3 patients experiences a DLT, up to 3 more patients are to be treated at that same dose level. If none of the additional 3 patients at that dose level experience a DLT, new patients may then be entered at the next higher dose level. However, if 1 or more of the additional 3 patients experiences a DLT, then no further patients are to be started at that dose level and the preceding dose is identified as the MTD. The MTD, therefore, is defined as the highest dose level at which none of the first 3 treated patients, or no more than 1 of the first 6 treated patients, experience a DLT.

If the starting dose of camidanlumab tesirine in combination with pembrolizumab is not tolerated, two lower doses could be investigated (Section 6.4). In such cases, if a DLT is observed in the first 3 patients enrolled in dose level -1, 3 additional patients will be enrolled; if 2 DLTs are observed out of these 6 patients, dose will be de-escalated to dose level -2.

Camidanlumab tesirine as monotherapy: The DLT (see Section 6.5 for further details) observation period for dose-escalation will be 21 days following the first study drug administration.

Camidanlumab tesirine in combination with pembrolizumab: The DLT (see Section 6.5 for further details) observation period for dose-escalation will start at the time of first administration of pembrolizumab and will end 21 days following this first administration of pembrolizumab.

Different dosing schedules of camidanlumab tesirine in combination with pembrolizumab may be tested in the dose-escalation part:

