5.5 Patient Replacements

Any patient in Part 1 who discontinues before completion of the first treatment cycle, for any reason other than a DLT, is to be replaced.

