6.2.2 Preparation and Administration

6.2.2.1 Camidanlumab Tesirine

The amount of the product to be diluted will depend on the dose level and the body mass of the patient. Of note, a cap on the administered dose is to be applied for patients with a body

mass index ≥ 35 kg/m²; these patients will be dose based on a body mass index of 35 kg/m². Additional details are included in the pharmacy manual.

Administration of camidanlumab tesirine will be performed by the Investigator or a qualified designee according to the pharmacy manual.

Camidanlumab tesirine is administered as a 30-minute intravenous (IV) infusion on Day 1 of each cycle.

Variations in infusion times due to minor differences in IV bag overfill/underfill and the institution's procedure for flushing chemotherapy lines will not result in protocol deviation.

Extravasation of camidanlumab tesirine may be associated with local irritation, swelling, pain, or tissue damage. The IV infusion site should be monitored for signs of IV infiltration or drug extravasation, and patients should be instructed to report immediately any signs of IV infiltration or drug extravasation during or after the infusion. Suspected extravasation of camidanlumab tesirine should be managed according to institutional protocol for management of extravasation of cytotoxic chemotherapy.

For patients who have a central line, administration of camidanlumab tesirine via this central line should be considered.

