6.2.2.2 Pembrolizumab

Pembrolizumab will be given as a fixed dose of 200 mg administered as a 30 minutes IV infusion (starting 1 hour after the end of the camidanlumab tesirine infusion).

Variations in infusion times due to minor differences in IV bag overfill/underfill and the institution's procedure for flushing chemotherapy lines will not result in protocol deviation.

For patients who have a central line, administration of pembrolizumab via this central line should be considered.

Please refer to prescribing information for further details, especially for monitoring of potential infusion reaction.

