Additional lower and/or intermediate dose levels to the provisional dose levels ([Table 5](#)) may be implemented (no change in pembrolizumab dose).

If one study drug, camidanlumab tesirine or pembrolizumab, is put on hold or discontinued due to related toxicity, the other study drug could continue as single agent.

In the dose-expansion portion of the study (Part 2), patients will be assigned to the RDE of camidanlumab tesirine in combination with pembrolizumab recommended from Part 1. The RDE selected for Part 2 will be based on review of all available study data and will be recommended by the DESC.

Table 5. Provisional Dose Levels in the Dose-Escalation (Part 1): Camidanlumab Tesirine in Combination with Pembrolizumab

Dose Level*	Dose of Cami	Dose of pembrolizumab
-2	13 µg/kg Q3W × 2	200 mg Q3W
-1	20 µg/kg Q3W × 2	200 mg Q3W
1	30 µg/kg Q3W × 2 (starting dose)	200 mg Q3W
2	45 µg/kg Q3W × 2	200 mg Q3W
3	60 µg/kg Q3W × 2	200 mg Q3W
4	80 µg/kg Q3W × 2	200 mg Q3W
5	100 µg/kg Q3W × 2	200 mg Q3W
6	125 µg/kg Q3W × 2	200 mg Q3W
7	150 µg/kg Q3W × 2	200 mg Q3W
8	200 µg/kg Q3W × 2	200 mg Q3W
9	250 µg/kg Q3W × 2	200 mg Q3W
10	300 µg/kg Q3W × 2	200 mg Q3W

* Additional or intermediate dose levels may be implemented during the study; however, the dose will not be higher than the highest dose of camidanlumab tesirine as monotherapy every three weeks (Q3W) investigated and deemed safe.

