6.5 Dose-Limiting Toxicities

For the dose-escalation of camidanlumab tesirine as monotherapy, a DLT is defined as any of the following events, which occur during the 21 days following the first study drug administration period of Part 1 (excluding the paired-biopsy cohorts), except those that are clearly due to underlying disease or extraneous causes.

For the dose-escalation of camidanlumab tesirine in combination with pembrolizumab, a DLT is defined as any of the following events, which occur during the 21 days following the first administration of pembrolizumab in Part 1, except those that are clearly due to underlying disease or extraneous causes.

A hematologic DLT is defined as:

Event	Severity
Febrile neutropenia or neutropenic infection	\geq Grade 3
Neutropenia lasting >7 days	\geq Grade 4
Thrombocytopenia	\geq Grade 4
Thrombocytopenia with clinically significant bleeding	\geq Grade 3
Thrombocytopenia requiring a platelet transfusion	\geq Grade 3
Anemia	\geq Grade 4
Anemia requiring transfusion	\geq Grade 3

A non-hematologic DLT is defined as:

Event	Severity
Hy's law case	Aspartate transaminase (AST) and/or alanine transaminase (ALT) $>3 \times$ upper limit normal (ULN) and bilirubin $>2 \times$ ULN, and without initial findings of cholestasis (serum alkaline phosphatase [ALP] activity $<2 \times$ ULN) and no other reason that could explain the combination of increased transaminases and serum total bilirubin, such as viral hepatitis A, B, or C, preexisting or acute liver disease, or another drug capable of causing the observed injury.
Hypersensitivity/infusion-related reaction (regardless of premedication)	\geq Grade 3. A Grade 3 hypersensitivity/infusion related reaction that resolves within 24 hours after onset with appropriate clinical management does not qualify as a DLT.
Radiculitis / Polyradiculopathy / GBS	\geq Grade 2
All other non-hematologic toxicity	\geq Grade 3

The following conditions **are not considered** DLTs:

Event	Severity
Fatigue	Grade 3 for \leq 7 days.
Diarrhea, nausea, or vomiting	Grade 3 in the absence of premedication that responds to therapy and improves by at least 1 grade within 3 days for Grade 3 events or to \leq Grade 1 within 7 days.
Alkaline phosphatase (ALP) and gamma glutamyl transferase (GGT)	Grade 3 ALP and GGT elevations, unless considered clinically relevant by the investigator.
Serum lipase or serum amylase	Grade 3 for \leq 7 days if without clinical signs or symptoms of pancreatitis.

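### In the combination escalation the DLT window opens at the first pembrolizumab dose, so the first camidanlumab tesirine infusion (Schedule 1) or the whole first cycle (Schedule 2) is outside the 3+3 count

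*Protocol*

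**What the plan says.** **Window, combination.** Protocol 4.1.1: the DLT "observation period for dose-escalation will start at the time of first administration of pembrolizumab and will end 21 days following" the first pembrolizumab administration. Protocol 6.5 defines combination DLTs as listed events "which occur during the 21 days following the first administration of pembrolizumab in Part 1". The two sections agree, so this is not a slip in one place.

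**Window, monotherapy.** Protocol 4.1.1: the period "will be 21 days following the first study drug administration".

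**Order of infusions.** The synopsis states that when both drugs are given, "camidanlumab tesirine will be administered prior to pembrolizumab, and separated by 1 hour". Protocol 6.2.2.1: "Camidanlumab tesirine is administered as a 30-minute intravenous (IV) infusion on Day 1 of each cycle". Protocol 6.2.2.2 has pembrolizumab "starting 1 hour after the end of the camidanlumab tesirine infusion". A footnote to Table 2 allows a longer gap if clinically indicated. Under Schedule 2 (4.1.1), pembrolizumab starts in Cycle 2.

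**Listed event.** Protocol 6.5 lists Grade 3 or higher hypersensitivity or infusion-related reactions as DLTs, whether or not premedication was given. A Grade 3 reaction that resolves within 24 h with appropriate management is exempt.

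**Replacement and continuation.** Protocol 5.5: a Part 1 patient who discontinues before completing the first cycle "for any reason other than a DLT, is to be replaced". Protocol 6.4: if one drug "is put on hold or discontinued due to related toxicity, the other study drug could continue as single agent".

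**SAP.** Section 4.9.1.2 takes the DLT definition from Protocol 6.5, 4.1.2 repeats the DLT-evaluable set of Protocol 9.2, and 3.3 records no modifications.

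**The concern.** Pembrolizumab is fixed at 200 mg, and camidanlumab tesirine is the drug whose dose the 3+3 is choosing. A window tied to the second drug leaves the start of exposure to the escalated drug uncounted. The infusion-reaction row in 6.5 shows the mismatch. Only camidanlumab tesirine has required premedication (6.9.1; none is required for pembrolizumab under 6.9.2), so wording that disregards premedication points to reactions to camidanlumab tesirine. Yet such a reaction during its first infusion precedes the window.

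DLT incidence is a primary endpoint. Each 3+3 decision turns on one or two events in three to six patients, so one uncounted event can change whether a level is passed and which dose is named the MTD. The same event in a monotherapy patient would be a DLT.

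**Working it through.** The plan gives no target DLT rate and no operating characteristics for the 3+3 (Protocol 9.1 and SAP 3.1 give patient numbers only), so there is no stated figure to reproduce. The check is one of timing and rules, followed by an illustration.

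**1. Length of the uncovered interval**
- Schedule 1: 0.5 h infusion + 1 h gap = 1.5 h, longer if the infusion is slowed or the gap extended. As a share of the time from first dose to window end: 1.5 / (1.5 + 21 × 24) = 0.3%. The share is small, but it contains the whole first infusion.
- Schedule 2: about 21 days, all of Cycle 1. First dose to window end is 21 + 21 = 42 days, so half is uncovered.

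**2. Events lost**
- Schedule 1: listed events with onset before pembrolizumab starts. In practice these are infusion reactions of Grade 4 or 5, and of Grade 3 not resolved within 24 h. Reactions with onset after pembrolizumab starts do count. The text does not settle an event that begins before and worsens after.
- Schedule 2: any listed event, hematologic or not, with onset in Cycle 1.

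**3. What happens to the patient**
- *Discontinues before the end of Cycle 1.* The reason is not a DLT, so 5.5 requires replacement. Under Section 6, a cycle starts with the first dose of either drug.
- *Continues on pembrolizumab alone (6.4).* The window then opens after the event, and the patient can complete it as DLT-free.
- *Never receives pembrolizumab.* No DLT period opens. The exclusion in Protocol 9.2 and SAP 4.1.2 covers only patients who leave the study during the DLT period, so it does not clearly remove this patient, who could sit in the denominator without a DLT.
- Under Schedule 2, 5.5 replaces patients lost in Cycle 1 but is silent on those lost in Cycle 2, where the DLT window lies.

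**4. Effect on passing a level (assumed rates)**

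Let *b* be the DLT rate after pembrolizumab starts among patients with no earlier event, and *a* the rate of listed events before it. A level is passed with 0/3, or with 1/3 followed by 0/3:

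P(pass) = (1 − q)³ + 3q(1 − q)⁵

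- All events counted: q = 1 − (1 − a)(1 − b)
- As written, patient replaced: q = b
- As written, patient kept as DLT-free: q = (1 − a)b

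Example, a = 2%, b = 20%: q = 1 − 0.98 × 0.80 = 0.216, and P = 0.784³ + 3 × 0.216 × 0.784⁵ = 0.482 + 0.192 = 0.674. As written with replacement: 0.8³ + 3 × 0.2 × 0.8⁵ = 0.512 + 0.197 = 0.709.

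| a (b = 20%) | q, all counted | P(pass), all counted | P(pass), replaced | P(pass), kept as DLT-free | Chance of ≥1 such event in 3 / in 6 |
|---|---|---|---|---|---|
| 0% | 0.200 | 0.709 | 0.709 | 0.709 | 0 / 0 |
| 1% | 0.208 | 0.691 | 0.709 | 0.713 | 0.030 / 0.059 |
| 2% | 0.216 | 0.674 | 0.709 | 0.717 | 0.059 / 0.114 |
| 5% | 0.240 | 0.622 | 0.709 | 0.730 | 0.143 / 0.265 |

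Varying b at a = 2%: all counted against replaced is 0.875 against 0.906 (b = 10%) and 0.466 against 0.494 (b = 30%).

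**The case against.** **Starting at pembrolizumab has a rationale.** It guarantees 21 days of observation on the combination under either schedule. That supports keeping the end of the window where it is. It does not require starting the count late.

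**Safeguards exist.** The combination dose may not exceed the highest monotherapy dose investigated and deemed safe (6.4), and monotherapy DLTs are counted from the first dose. The steering committee sets dose levels and the RDE/MTD on safety findings in all patients (4.1.3). Enrolment halts for a Grade 5 event or two non-hematologic Grade 4 events where relationship to either drug cannot be ruled out (4.3.2). Infusion reactions have their own line in the SAP's TEAE summary (4.9.1.1). All of this stands, and it limits harm to patients. None of it puts the event back into the 3+3 count or the DLT table, and a single Grade 4 reaction need not trigger the halt.

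**Such events look uncommon.** Protocol 1.3.4 reports 44 monotherapy patients in this trial at 20 to 150 µg/kg. The Grade 3 or higher terms seen in at least 5% do not include an infusion reaction or hypersensitivity. If that list is complete, any one such term occurred in at most 2/44 = 4.5%, over all cycles and including Grade 3 reactions that resolved quickly. This stands, and it is why the table stops at 5%.

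**Stronger readings that the documents do not support.** A reader might infer that no acute toxicity of camidanlumab tesirine can be a DLT. That is too broad, given the 24-hour exemption and the counting of later onsets. A reader might assume 10% of patients affected, which would put the pass probability at 0.54 instead of 0.71. Nothing in 1.3.4 supports that rate for infusion reactions. A reader might also infer that the trial will escalate into doses shown to be unsafe, but the monotherapy cap and committee review argue against this. Nor is loss of comparability with monotherapy a serious harm in itself, since no comparison or hypothesis test is planned (SAP 4).

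**Conclusion.** The concern holds in a bounded form. On the plain text of 4.1.1 and 6.5, listed events between the first camidanlumab tesirine dose and the first pembrolizumab dose are not DLTs, and nothing in the protocol or SAP repairs this. The affected patient is either replaced or can be counted as DLT-free.

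Under Schedule 1 the gap is about 1.5 h and bears on severe acute reactions. With an assumed 20% in-window rate, it changes the pass probability by nothing at a 0% event rate and by 0.09 at 5% (0.709 against 0.622). Under Schedule 2 the gap is a full cycle of the escalated drug. The documents give no rate from which to size that effect. All pass probabilities rest on assumed rates. The gap in the wording does not.

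This is worth correcting but not critical for Schedule 1. It becomes important if Schedule 2 is opened.

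**What to change.** Reconcile Protocol 4.1.1, 5.5, 6.5 and 9.2 with SAP 4.1.2 and 4.9.1.2:

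- Define the combination DLT period as running from the first dose of any study drug to 21 days after the first pembrolizumab dose.
- State that a patient with a listed event before pembrolizumab, including one who therefore never receives it, counts as having a DLT, is DLT-evaluable and is not replaced.
- Tie the replacement rule in 5.5 to the DLT period rather than to Cycle 1, so that it also works under Schedule 2.
- Use the same period in the SAP's DLT-evaluable set and DLT table.

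The listed DLT events, doses, schedules and treatment rules stay as they are. No new assessments are needed, because adverse events are collected from consent (Protocol 8.2). The cost is a few sentences in four protocol sections and two SAP sections, and a DLT rate that may look slightly less favourable.

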4.1.2 Dose-Expansion

Two groups are planned in the dose-expansion part (Part 2):

- Group 1: an indication for which camidanlumab tesirine in combination with pembrolizumab was shown in Part 1 to have preliminary activity.
- Group 2: a basket group of patients with advanced solid tumors and MSI-H/dMMR status, who have received a prior regimen containing a PD-1/PD-L1 inhibitor, for which the best response was CR, PR, or SD ≥ 4 months, and then progressed while under treatment with a PD-1/PD-L1 inhibitor based regimen; no more than 4 patients with the same indication are allowed in this basket group.

Part 2 will enroll approximately 30 patients, approximately 16 patients in Group 1 and 14 in Group 2.

4.1.3 Safety Oversight by the Dose-Escalation Steering Committee

A DESC will be responsible for safety monitoring and overall supervision of the study. Membership of the DESC will include:

- Medical Monitor(s) (Sponsor and/or designee)
- Investigator(s) from each participating site
- *Ad hoc* members (e.g., project manager, study coordinator(s), regulatory representative(s), pharmacovigilance representative(s), biostatistician(s), clinical pharmacologist(s), etc.)

In general, the DESC will make any substantial decisions regarding the conduct of the study, such as:

- Monitor the safety of the study and review its progress at monthly intervals or more frequent intervals as required.
- Determine dose levels to be administered and the RDE/MTD based on assessment of safety findings in all patients and determination of DLTs in dose-escalation cohorts.
- Provide input into protocol changes, when required.
- Determine if it is appropriate to maintain a Q3W schedule or test other dosing regimens.
- Determine whether adjustment in timing of on-treatment biopsy and other [REDACTED] sample(s) is needed based on emerging evidence.

Each DESC meeting and the decisions made will be documented in writing and provided to all participating DESC members and Investigators. Meeting documents may be submitted to IRBs/IECs or competent authorities according to institutional or local requirements.

The DESC may be maintained during Part 2 (expansion) of the study to continue to monitor and evaluate patient safety, but the frequency of meetings can be adjusted.

4.2 Study Periods

4.2.1 Screening Period

Informed consent must be obtained for each patient and documented with a signed informed consent form (ICF) prior to any study procedures. Procedures that are performed as part of standard of care (SoC) may be used to satisfy screening requirements if they are performed in the appropriate window.

The screening period is from 21 days to 1 day prior to the start of the study drug. The screening assessments should be performed within this period in order to assess the eligibility of the patient against the inclusion and exclusion criteria (Sections 5.1 and 5.2, respectively).

See Section 5.3 for the information to be collected on screening failures.

4.2.2 Treatment Period

The treatment period starts on the date when a patient receives the first dose of study drug and continues until end of treatment visit.

A treatment cycle is defined as 3 weeks (i.e., 21 days).

After completion of Cycle 4, the Day 8 visit is not required unless clinically indicated.

Patients may continue treatment for up to 1 year or until disease progression, unacceptable toxicity, or other discontinuation criteria (Section 5.4), whichever occurs first. Additionally, patients benefiting clinically at 1 year may continue treatment after a case by case review with the Sponsor.

4.2.3 End of Treatment

An EOT visit should be performed as soon as possible after the decision to discontinue the study drug, preferably within 30 days after last dose of study drug, and before initiation of any new anticancer treatment.

When EOT coincides with a scheduled visit, the scheduled visit will become EOT.

